#### **Completion criteria to treatment with CPAP/BiPAP:**

- Respiratory improvement that it leaves to change a conventional oxygen system or OHF.
- Lack of tolerance of non-invasive ventilation.
- Worsening of respiratory failure defined by PaO2/FiO2 < 100, 20% increase from baseline (if basal pCO2 > 40 mmHg), sustained signs of distress, SaO2 < 90% or Glasgow < 15, in patients without non-intubation orders.
- Death of the patient.

### **Follow-up to discharge**

#### **Day 30**

It will be verified if the patient has been discharged, absence of complications and readmissions, recording residual dyspnoea and Barthel index by telephone control.

#### **Day 90**

It will be verified if the patient has been discharged, absence of complications and readmissions, recording residual dyspnoea and Barthel index by telephone control.

## **STADISTICS ANALYSIS**

A part of analysis is carried out using IBM SPSS 25.0 software (SPSS, Chicago, Ill) and the other part by Butler Scientifcs, an external statistical company.

Qualitative variables are expressed as a percentage and are compared using a chi-square study. The quantitative ones are expressed as means or medians with interquartile range and statistical studies are carried out using parametric and non-parametric tests. Demographic and clinical variables are analysed at admission, while analytical, blood gas variables and vital signs are analysed in each of the controls comparing non failure of high flow therapy group with non-invasive ventilation group (CPAP/BIPAP). The same analyses are performed between the CPAP and BIPAP treatment subgroup. A predictive model of OHF failure and non-invasive ventilation failure will be developed using logistic regression or multivariate Cox regression, depending on the case.

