### Admission in RICU

The patient is included in the study after signing informed consent. In this moment, a blood sample is obtained and vital constants of patient like respiratory rate (RR), heart rate (HR), EKG signal, Oxygen Saturation (SaO2) and blood pressure start to be monitored continuously. Barthel index and dyspnoea grade of MRC scale are registered.

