### Standard support with Oxygen High Flow (OHF)

#### Day 1

All patients start respiratory support with oxygen high flow system (AIRVO2 or V60 plus), if it doesn't exist contraindications.

Initial parameters: Temperature 34-37°C, flow 30 l/min and FiO2 100%. Then the flow will be progressively increased until the respiratory rate is less than 35, and the FiO2 will be progressively reduced until the minimum concentration to maintain SaO2 greater than 96%. Arterial blood gas analyses and record of vital constants will be performed at 1h, 4h, 6h and 12h after starting high flow therapy.

#### Day 2

24h after starting high flow therapy a new arterial blood gas analyses and record clinical parameters will be performed. If the therapy parameters like FiO2 or flow have been modified it will also be recorded.

#### Day 3

48h after starting high flow therapy control includes arterial gasometry, blood analyses and record clinical parameters, vital constants and therapy parameters.

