## **Treatment with non-invasive ventilation (CPAP or BiPAP)**

### **Interventional group**

#### **Day 1**

Patients with lack of tolerance to OHF or worsening of respiratory failure with oxygen high flow support are switched to treatment with non-invasive ventilation. Patients are randomized to CPAP or BiPAP ventilatory mode.

The treatment duration is at least 18 hours a day. Initial pressure is 8-10 cmH2O in CPAP group and 16/10 cmH2O in BiPAP group, although it will be increased progressively (from 10 to 12 or 15 cmH2O in cpap group and from 16/10 to 18/12, 20/15 and 22/16 in BiPAP group) until the respiratory rate is lower than 30, and SaO2 > 93%. Initial FiO2 is 100% in both groups, and it will be progressively reduced until the minimum concentration to maintain SaO2 greater than 96%.

Arterial blood gas analyses and record of vital constants will be performed at 1h, 4h, 6h and 12h after starting high flow therapy specifying ventilation parameters.

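### Neither failure model has a specified predictor list, selection rule, shrinkage, internal validation or performance measure, so its apparent fit could be materially optimistic

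*Combined protocol and SAP*

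**What the plan says.** The section STADISTICS ANALYSIS closes with the only text on the models: "A predictive model of OHF failure and non-invasive ventilation failure will be developed using logistic regression or multivariate Cox regression, depending on the case". It does not say which variables may enter, how they are chosen, at what time they are measured, how many events are expected, or how performance will be judged. It mentions no penalisation, cross-validation or bootstrap.

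The same section describes between-group comparisons. For the repeated measurements it says that "analytical, blood gas variables and vital signs are analysed in each of the controls comparing non failure of high flow therapy group with non-invasive ventilation" patients. The comparisons are then repeated for CPAP against BiPAP. Baseline characteristics are handled separately: "Demographic and clinical variables are analysed at admission". Part of the analysis goes to an external company whose methods are not described.

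The data behind this are repeated measurements. At admission, monitoring starts for "vital constants of patient like respiratory rate (RR), heart rate (HR), EKG signal, Oxygen Saturation" and blood pressure, and "Barthel index and dyspnoea grade of MRC scale are registered". On OHF, "Arterial blood gas analyses and record of vital constants will be performed at 1h, 4h, 6h and 12h after starting high flow therapy", with further controls at 24 h, 48 h and the last day of therapy. Entry to NIV is by failure of OHF: "Patients with lack of tolerance to OHF or worsening of respiratory failure with oxygen high flow support are switched to treatment with non-invasive ventilation".

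**The concern.** A regression fitted and judged on the same patients looks better than it will in new ones. The gap grows with the number of candidate predictors and shrinks with the number of events. This plan limits neither and names no step that would measure or correct the gap.

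Two features make this more than a formality. First, patients enter the NIV group by failing OHF, so the comparison of non-failures with the NIV group is close to a one-variable-at-a-time test against the outcome of the first model. Nothing in the plan stops those results from choosing the predictors. Second, the NIV model starts from the OHF failures alone, in one unit, so it has the smaller data set.

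At stake are the credibility of both models and of any predictor singled out as important. They are the only multivariable analysis planned.

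**Working it through.** **The plan's own figures.** There are none to reproduce. The documents give no sample size, event count, number of predictors or target performance.

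**Possible predictor pool on OHF.** From Admission in RICU, leaving out the EKG signal, the numeric vital signs are respiratory rate, heart rate, SaO2 and blood pressure: 4. From the OHF section, the controls that name vital constants are 1, 4, 6, 12 and 48 h and the last day: 6. The 24 h control lists gases and clinical parameters but does not name vital constants, so it is not counted.

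4 × 6 = 24 values, before gases, bloods, demographics, Barthel index and MRC grade. Without the last-day control it is 4 × 5 = 20. This pool is available, but the plan does not state it as the predictor set.

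**Events.** If E patients fail OHF and switch, at most E enter the NIV model, and its events are a fraction of E. As an illustration with an assumed 40% failure rate at each step, 150 patients give 0.4 × 150 = 60 OHF failures. If all 60 switch, there are 0.4 × 60 = 24 NIV failures.

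**Simulation.** All inputs are assumptions:
- independent normal predictors, of which 3 are real and the rest noise;
- event rate about 40% and true AUC about 0.73;
- logistic regression with all candidates entered and no shrinkage beyond a numerical stabiliser;
- 200 replicates per setting.

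Optimism = mean apparent AUC − mean AUC in new patients. Events per candidate = 0.4n/p, for n patients and p candidates.

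| Patients (events) | Candidates | Events per candidate | Apparent AUC | New-patient AUC | Optimism |
|---|---|---|---|---|---|
| 75 (30) | 5 | 6.0 | 0.770 | 0.701 | 0.07 |
| 75 (30) | 24 | 1.2 | 0.905 | 0.612 | 0.29 |
| 75 (30) | 48 | 0.6 | 0.993 | 0.577 | 0.42 |
| 150 (60) | 5 | 12.0 | 0.753 | 0.713 | 0.04 |
| 150 (60) | 10 | 6.0 | 0.769 | 0.697 | 0.07 |
| 150 (60) | 24 | 2.5 | 0.825 | 0.662 | 0.16 |
| 300 (120) | 24 | 5.0 | 0.780 | 0.691 | 0.09 |
| 600 (240) | 5 | 48.0 | 0.734 | 0.727 | 0.01 |
| 600 (240) | 24 | 10.0 | 0.753 | 0.709 | 0.04 |

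Optimism runs from negligible to severe, depending on the two quantities the plan omits. Overfitting also costs real performance. At 60 events, going from 5 to 24 candidates raises the apparent AUC from 0.753 to 0.825 while the AUC in new patients falls from 0.713 to 0.662.

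**The case against.** The strongest reply is that the plan is silent rather than wrong. A reader might infer that it will screen dozens of variables by p-value, fit them without any safeguard and report an inflated c-statistic. The documents do not support that reading:
- The variables tested at each control belong to the group comparisons. The modelling sentence stands apart and names no predictor set, screening step or threshold.
- No c-statistic or other performance measure is promised.
- Shrinkage and validation are unspecified, which is not the same as excluded, and the external company may apply them.
- Some optimism exists in every fitted model. Whether it matters depends on event and predictor numbers that nobody can read from the text.

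The size can also be overstated. Calculations in which every predictor is noise give an apparent AUC of about 0.63 with 10 predictors, 200 patients and 80 events, an optimism of 0.63 − 0.50 = 0.13. With three real predictors and 200 patients, simulated optimism is 0.045 with 10 predictors and 0.019 with 5. Respiratory rate and SaO2 are part of the plan's definition of worsening on OHF, so they are hardly noise. Serial readings are correlated, which weakens the effect of a univariable screen. With 24 noise candidates, 100 patients and 40 events, the apparent AUC after screening falls from 0.66 to 0.62–0.64 when repeats of a sign correlate at 0.5–0.7.

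All of this stands as a limit on certainty and size. It does not remove the gap. A plan that promises predictive models and sets no bound on candidates and no check on optimism leaves the unfavourable cases open. The remedy does not need the missing event count, because a bootstrap shows little optimism if data are ample and exposes it if they are not.

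**Conclusion.** The concern holds as a gap in specification with a conditional consequence. For both models the plan leaves open the candidate list, selection rule, shrinkage, internal validation and performance measure. If many of the repeated measurements are considered against few events, the coefficients and apparent performance will be materially optimistic, and the NIV model is the more exposed.

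The size cannot be fixed from the documents. Under the assumed logistic setting, AUC optimism is about 0.01 with 240 events and 5 candidates, about 0.16 with 60 events and 24 candidates, and up to 0.42 in the extreme case of 30 events and 48 candidates. These figures rest on assumed event rates, effect sizes and independent predictors, and Cox models were not simulated. A claim that reported discrimination is certain to be inflated would go beyond the text. The randomised comparison of CPAP with BiPAP does not depend on these models.

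**What to change.** In STADISTICS ANALYSIS, for each model:

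1. State the outcome, the rule for choosing logistic or Cox regression, and the expected number of events.
2. Fix a short list of candidate predictors before looking at outcomes. Measure all of them at baseline or at one set early control before failure, and state how patients who fail earlier are handled. Exclude the last-day control, which can coincide with failure.
3. State that predictors will not be chosen from the between-group p-values.
4. Bootstrap the whole model-building process, for example with 500 resamples. Report optimism-corrected discrimination and calibration slope beside the apparent values.
5. If optimism is material, shrink the coefficients by the bootstrap slope or use penalised regression. The choice of penalty is secondary.
6. Require the external company to follow the same specification.

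Before a predictor time is set for the NIV model, the Day 1 control times in the NIV section need to be reconciled, since they are written as counted from the start of high flow therapy.

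The cost is some added wording and a few hours of analysis. Reported performance will look less favourable. No new data are needed and no treatment changes.
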